## Sampling

**Sample and procedure for inclusion of patients in the unexposed cohort.**

In order to carry out an analysis of the new care model (functional recovery programme and patient follow-up through a digital application), the entire simple universe will be included, a complete cohort analysis, with follow-up at 1, 3, 6 and 12 months using a digital toolFollow-up will be carried out at 6 weeks, 4 months and 12 after discharge according to the protocol of the orthogeriatrics unit.

The patient will be given instructions on how to download the application to their mobile device. The application is available in the open repository of mobile applications for public use. Once the app is installed, the patient will be provided with a personal access code that does not include recognisable personal data. This code will be used to connect to the therapeutic plan and to the questionnaires provided by the patient when registering with the Traumatology Service. Only the principal investigator (PI) will have a system of correlation between the code and the patient's personal data, be responsible for its safekeeping.

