### Specific objectives

- To describe the improvement in gait ability in patients undergoing hip surgery after a functional recovery programme compared to the historical control group (exposed cohort).
- To describe the clinical and functional characteristics of the patients operated on for hip fracture in the SJD hospital in León who are being followed up by the new system of care implemented in comparison with the historical control group (exposed cohort).
- To analyse risk and protective factors related to the level of dependency and mortality at 30 days and one year of follow-up in patients operated on for hip fracture at the SJD hospital in León.
- To describe the impact of a functional recovery programme on the prevention and treatment of sarcopenia in the new unexposed cohort.
- To describe the quality of life and patient-reported outcomes in the new unexposed cohort.
- To analyse the impact of a functional recovery programme on the prevention of falls in elderly patients who have undergone hip fracture surgery.

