## METHODOLOGY

### Study design

Longitudinal analytical observational study of ambispective cohorts with two groups, an exposed cohort (retrospective) and a non-exposed cohort (protective factor), made up of people over 65 years of age referred from the Emergency Department of the University Care Centre of León (CAULE) to the Hospital San Juan de Dios de León (HSJD) with a confirmed diagnosis of hip fracture and who underwent hip fracture surgery in the latter during the years 2020 and 2021, and who will be followed up during the year after surgery, in the latter, to undergo hip fracture surgery during the years 2020 and 2021 and who will be followed up during the year following the surgery.

Two groups:

- Non-exposed cohort (protective factor): group of patients operated on during the year 2021 in HSJD for hip fracture and to which the new programme implementing functional recovery and therapeutic exercise will be applied with follow-up for one year. The implementation of a functional recovery plan and subsequent follow-up is considered a protective factor in relation to the loss of functionality.
- Exposed cohort (retrospective): complete cohort of patients operated on during the year 2020 in HSJD for hip fracture and to whom no specific functional recovery plan was applied.

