#### **Variables**

In the two groups that form part of this study, different variables specified in the database adapted from the National Hip Registry and the *International Fragility Fracture Network*, of which the HSJD is a member, will be collected.

Until now, data collection and patient follow-up was completed after one month and the data was transferred annually to the National Hip Fracture Register. In the new model proposed by orthogeriatrics unit of the HSJD, patients will be followed up in person at one and a half months, four months and one year, and at discharge, one month after discharge, three months, six months and one year, by means of a digital application.

The variables to be collected are described below:

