- Level 2: non-functional ambulation. Walking with great physical assistance from a person, and/or walking is only possible within a therapy session at home, or in hospital, between parallel bars
- Level 3: ambulation in the home, walking with light physical contact with a person. Is able to walk only indoors, on flat, horizontal surfaces, usually within a defined area.
- Level 4: walks autonomously in the home or neighbourhood environment, but needs supervision by a person. They can walk on uneven surfaces and can climb an occasional step.
- Level 5: independent community walking. Can walk on uneven terrain, up and down steps, ramps, kerbs, etc. Can walk considerable distances, but with obvious limp.
- Level 6: walks normally both indoors and outdoors, in the absence of a limp or other abnormality.

This scale is administered at admission, 6 weeks, 4 months and 1 year.

**Second group: the variables collected in this second section form part of the new model of care established by the orthogeriatric service, whereby the hip fracture patient will be followed up for up to one year after the intervention, therefore, they are variables that can only be measured in the cohort of unexposed patients.**

Patient follow-up variables (Table II):

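### The in-person visits are timed from discharge but the follow-up year from surgery, so time since surgery at each visit and the start of the mortality window are not fixed

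*Combined protocol and SAP*

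**What the plan says.** **Discharge as the origin.** For the unexposed (2021) cohort, the Sampling section states that in-person follow-up "will be carried out at 6 weeks, 4 months and 12 after discharge"; the 12 is evidently months. The Variables section lists the app contacts as "at discharge, one month after discharge, three months, six months and one year". There, discharge is attached explicitly only to the one-month contact, and the in-person visits carry no origin.

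**Surgery as the origin.** Study design refers to patients "who will be followed up during the year after surgery" and repeats the point as "who will be followed up during the year following the surgery". The introduction to the second group of variables, just before Table II, says that the patient "will be followed up for up to one year after the intervention".

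**No origin.** Table III and the notes under each scale give nominal times only. One specific objective concerns "mortality at 30 days and one year of follow-up", without saying when follow-up begins. For the earlier care model, which covers the exposed (2020) cohort, the Variables section says that "data collection and patient follow-up was completed after one month", again without a start.

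**Deaths before discharge.** The eligibility section lists death by hospital discharge among the withdrawal criteria for the 2021 cohort. It lists no withdrawal criteria for the 2020 cohort. No section says whether a withdrawn patient's death still counts in the mortality analysis.

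**The concern.** Functional recovery after hip fracture surgery depends on time since the operation. If visits are timed from discharge, two patients seen at the same nominal visit have had different recovery times whenever their stays differ. Results labelled 6 weeks or 4 months then mix recovery with length of stay, and without recorded dates the two cannot be separated later. Table I lists neither a surgery date nor a discharge date.

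For mortality, the origin decides which deaths are in the window. A 30-day window from surgery includes in-hospital deaths. One from discharge excludes those before discharge and extends later. If the two cohorts are handled differently, by clock or by the one-sided withdrawal rule, the two mortality figures do not measure the same thing.

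**Working it through.** The plan gives no figure to reproduce, so the check sets the sections side by side and works out what a discharge clock implies.

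**1. Can the sections be reconciled as written?** A visit 12 months after discharge falls on day 365 + L after surgery, where L is the postoperative stay in days. A follow-up year that starts at surgery ends on day 365. For any L above zero, the last visit lies L days outside the stated period. No section resolves this or sets visit windows.

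**2. Time since surgery at each visit.** Formula: days since surgery = nominal day + L. Nominal days are 42 (6 weeks), about 122 (4 months) and 365 (12 months). L is an assumption, 5 to 20 days, because the documents give no length of stay.

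| Visit | Surgery clock | Discharge clock, L = 5 | Discharge clock, L = 20 | Shift as share of nominal interval |
|---|---|---|---|---|
| 6 weeks | 42 | 47 | 62 | 5/42 = 12% to 20/42 = 48% |
| 4 months | 122 | 127 | 142 | 5/122 = 4% to 20/122 = 16% |
| 12 months | 365 | 370 | 385 | 5/365 = 1.4% to 20/365 = 5.5% |

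These are shifts for one patient. A difference between cohorts would depend on the difference in mean stay, on which the documents give nothing.

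**3. The 30-day mortality window, if follow-up starts at discharge.** It runs from day L to day L + 30 after surgery: days 5 to 35 for L = 5, and days 20 to 50 for L = 20. It loses the days before discharge and gains the same number afterwards.

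To scale the deaths lost, assume a constant hazard and 30-day mortality from surgery of m = 3% to 10% (also an assumption). The probability of death before discharge is 1 − (1 − m)^(L/30).

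- m = 3%, L = 5: 1 − 0.97^(5/30) = 0.0051, or 17% of the 30-day deaths; 67 × 0.0051 = 0.3 deaths per 67 patients.
- m = 10%, L = 20: 1 − 0.90^(20/30) = 0.0678, or 68% of the 30-day deaths; 67 × 0.0678 = 4.5 deaths per 67 patients.

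The 67 is the sample mentioned under Analysis of results and serves only as a scale. These counts leave out the deaths gained at the far end of the window. Under the same constant hazard, 30-day mortality among patients discharged alive is again m, so the shift alone does not lower the rate.

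**4. The withdrawal rule taken alone.** Suppose the clock starts at surgery but patients who die before discharge are removed. Under a constant hazard, 30-day mortality among the rest is 1 − (1 − m)^((30 − L)/30). With m = 5% and L = 10 this is 1 − 0.95^(20/30) = 3.4%, against 5% with all deaths counted. Setting time zero without addressing the withdrawal rule would therefore leave the asymmetry in place.

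**The case against.** The strongest reply is that this is a wording point with little to act on.

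- Only the Sampling section ties the in-person visits to discharge, and the surgery-based statements describe total duration, not visit times. That is correct and narrows the contradiction. It does not remove it, because the 12-month visit still falls outside the year from surgery and nothing says which origin governs analysis.
- A reader might infer that length of stay will create or hide a functional difference between 2020 and 2021. The documents do not support this. Earlier follow-up ended at one month, and the second-group variables are said to be measurable only in the 2021 cohort. There appears to be little or no 2020 functional data at the later visits to distort. Shorter stay is a general aim of the hospital process, not described as new in 2021.
- A reader might also infer that a discharge clock would make 2021 mortality lower by definition. That does not follow. No section times mortality from discharge, the 2020 origin is unstated, and the shifted window gains later days as it loses early ones. A lower rate from the shift alone would need a hazard that falls after surgery, which the documents do not quantify.

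The reply does not reach the withdrawal criterion. It is written for one cohort only and bears directly on whether in-hospital deaths are counted.

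**Conclusion.** The point holds in a limited form. The time origin is contradictory, and the mortality objective and Table III leave it open. Under the discharge clock, nominal visits are not at a common time since surgery: for an assumed stay of 5 to 20 days, the 6-week visit falls on days 47 to 62. The effect is largest at that visit and small at 12 months.

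The mortality consequence of the clock is conditional on reading follow-up as starting at discharge. The one-sided withdrawal rule is a separate route by which in-hospital deaths could count in 2020 and not in 2021; it rests on the eligibility text and on the absence of any statement that withdrawn patients' deaths are retained. The size of any distortion between cohorts cannot be derived, because the documents give no length of stay or mortality for either cohort; the ranges above are illustrative. This should be settled before analysis, as it is cheap to correct now and hard to repair if dates are not recorded.

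**What to change.** 1. State that date of surgery is time zero for analysis in both cohorts.
2. Leave the clinic visits where the unit's protocol puts them. Record surgery, discharge and assessment dates, derive days since surgery (assessment date minus surgery date), and analyse mobility by that variable.
3. Define 30-day mortality from surgery in both cohorts, with deaths before discharge counted as events. Define 1-year mortality the same way where 2020 vital status is available.
4. State that meeting the 2021 withdrawal criterion for death by discharge does not remove the patient from the mortality analysis.
5. Reconcile Specific objectives, Study design, the 2021 eligibility criteria, Sampling, Variables, the introduction to the second group of variables, and Table III.

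**Cost.** Wording in those sections, three recorded dates and one derived variable. Some visits will fall outside windows centred on the nominal day since surgery. The availability of 2020 surgery and death dates must be confirmed: Table I lists neither, death appears only among the follow-up variables said to be measurable in the 2021 cohort alone, and earlier follow-up ended at one month. If 1-year vital status for 2020 cannot be obtained, 1-year mortality should be reported for 2021 alone and described as such.

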#### **Sample and procedure for inclusion of patients in the exposed cohort.**

Data will be collected from the medical register reported annually from the HSJD to the National Hip Fracture Registry as part of the active research project in which the project investigators linked to the HSJD are involved.

#### **Variables**

In the two groups that form part of this study, different variables specified in the database adapted from the National Hip Registry and the *International Fragility Fracture Network*, of which the HSJD is a member, will be collected.

Until now, data collection and patient follow-up was completed after one month and the data was transferred annually to the National Hip Fracture Register. In the new model proposed by orthogeriatrics unit of the HSJD, patients will be followed up in person at one and a half months, four months and one year, and at discharge, one month after discharge, three months, six months and one year, by means of a digital application.

The variables to be collected are described below:

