According to clinical practice guidelines, rehabilitation should begin from the moment of admission, following a multidisciplinary approach, where all those involved are aware of the treatment plan and reasonable expectations of recovery (10-13,16). Early mobilisation, weight bearing and active recovery are the basis of rehabilitation treatment, resulting in lower mortality six months after the intervention and better ambulation (17).

It is estimated that 60-80% of elderly people with hip fractures were walking independently before the fracture. One of the most important goals is to achieve the same degree of ambulation as before the fracture. For this reason, it is important to use validated scales that can provide information on the patient's previous state and help to assess whether or not the objectives have been achieved. Despite this, only 50% manage to recover their pre-fracture state (10).

To achieve this goal, it is desirable that the patient be operated on as soon as possible and begin sitting up the day after surgery, thus facilitating early loading as soon as possible, provided that drains or other devices permit (10,11).

Specific rehabilitation treatment will aim to increase joint mobility; strengthening of the gluteal and quadriceps muscles; re-education of walking as soon as possible, first with the use of devices and progressively more and more independently (10).

In recent years, several reviews have studied the implementation of different rehabilitation programmes for the elderly after hip fracture, with the aim of increasing physical and psychosocial function (18-23).

Several of these reviews (18,19,21) have focused on comparing multidisciplinary rehabilitation with routine orthopaedic care after hip fracture. These studies found that multidisciplinary rehabilitation was associated with a modest but significant reduction in adverse outcomes such as death. These results were confirmed by Wang et al. (22) who found significant differences in terms of reduced mortality during hospitalisation or during subsequent follow-up.

While rapid surgery, early mobilisation and a multidisciplinary team-based approach to rehabilitation seem important for restoring the patient's previous function, there are discrepancies about the contribution of various components of this intensive approach to interventions specifically focused on improving independence such as dressing, shopping and interacting in the community (18,21,24).

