### **Justification of the Study**

In recent years there has been an increase in the number of hip fractures and this is expected to continue until 2050. From 1.26 million in 1990 to 21.3 million in 2050 (28). Given the ageing of Western populations, the total number of hip fracture cases and their economic consequences are likely to increase considerably. This, coupled with the negative outcome for survivors, many of whom end up being more dependent than before the fracture, calls for studies that address the effectiveness of a functional recovery programme that addresses both the physical and psychosocial spheres of the patient, both in and out of hospital.

The target population of this study is an ageing population, living in a rural environment, far from relatives or people who can help them with daily tasks and with difficulties in accessing the different resources to achieve an optimal recovery. These people therefore need a level of functional recovery that can give them back the level of independence they had before the hip fracture.

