#### **First group: variables established in the National Hip Fracture Registry, defined according to its protocol**

These scales will be administered to both groups:

- Cohort of unexposed patients: to be administered on the dates indicated.

- Cohort of exposed patients (retrospective): data will be retrieved from the Exceldata collection system that the medical management of the HSJD manages for the follow-up of these patients and the report to the national hip fracture registry.

These variables include socio-demographic, clinical and functional characteristics prior to surgery (Table I):

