Gait is the parameter most strongly associated with frailty states, with gait speed being the parameter most commonly associated with frailty(34,36). This is why it is so important to recover functions and capacities in this area of movement. This scale is very easy to use and apply and is used by the national fracture registry, which allows us to make comparisons and statistical analyses with the results published with this registry.

It assesses by ability levels ranging from 0 to 11. Its design allows firstly to determine gait ability and secondly to see the evolution and establish treatment guidelines.

Capacity levels:

- Level 1-Independent mobility inside and outside the home without technical aids
- Level 2- Independent mobility inside and outside the home, with technical assistance.
- Level 3- Independent mobility inside and outside the home with two technical aids or walker.
- Level 4- Independent mobility only indoors without technical assistance.
- Level 5- Independent mobility only indoors with a technical aid.
- Level 6- Independent mobility only indoors with two technical aids or walker.
- Level 7- Independent mobility only within the house under personal supervision.
- Level 8- Mobility only within the home with little assistance from a person.
- Level 9- Mobility only within the home with a lot of help from a person.
- Level 10- Mobility with two people or no mobility.
- Level 11- Unknown.

For simplicity this variable is summarised in these questions:

- Technical aids (yes/no).
- Outside/inside the home.
- And note the best situation, i.e. it is better with a cane outside than without help at home.

This scale is administered at admission, 6 weeks, 4 months and 1 year.

• ***ModifiedFunctionalAmbulatoryClassifier(mFAC)(36).***

It is a scale that assesses different levels of ability by grading them between 0 and 6. Its design allows firstly to determine gait ability and secondly to see the evolution and establish treatment guidelines. The modified gait assessment scale has shown an intraclass correlation coefficient(ICC)= 0.960, with a 95% confidence interval: 0.942-0.972, an inter-observer agreement Cohen's kappa index of 0.83 (CI: 0.69-0.97) and a validity p= 0.814 (36-38)

The capacity levels for this scale are:

- Level 0: Patient who cannot remain seated for more than 1 minute without the help of the backrest and armrest.
- Level 1: Patient who can remain seated without the aid of the backrest and armrest for more than 1 minute.

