**Data collection procedure.**

The clinical data of the exposed cohort corresponding to the patients operated on during the year 2020 will be extracted from the data collection records that the medical directorate manages for the follow-up of these patients and the report to the National Hip Fracture Registry.

The clinical and care data of the unexposed cohort of patients who will undergo surgery in 2021 will be collected by the trauma team during scheduled patient follow-up visits and by the patient or the patient's caregiver using a mobile application. This data will be recorded and the PI will be responsible for the safekeeping and processing of the data in accordance with current legislation.

The present study is part of a global project to monitor the cohort of patients with hip fractures operated on at the HSJD. This project is a "*real world data*" study in which all the variables of routine practice are collected through a technological application that allows the clinical situation of the patient to be known in real time. The information will be collected through the Caaring® app, developed by Persei Vivarium, with the specific programme for the care of hip fracture patients.

The patient, or the responsible person in patients with cognitive impairment, will receive instructions on how to download the mobile application to their device from an open repository of publicly available mobile applications. The patient will be provided with an access code in which no recognisable data is included. This code allows connection to the questionnaires and information provided by the HSJD trauma service. Only the PI will have a system of correlation between the code and the patient's personal data, and will be responsible for its safekeeping.

The app has two different profiles (doctor, patient), with the researchers being able to enter the data from the face-to-face assessments and the patient or main caregiver the follow-up data from home.

The specialist who monitors the patient has a control panel on the web-app, where he/she has access to risk alerts generated by the system based on the data collected and the clinical rules established for this purpose.

Content of the tool:

The tool has two types of content:

- Questionnaires for the collection of data on the clinical, functional and quality of life evolution of the patient as shown in table III.

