**Table III. Summary of variables, assessment instruments and collection period**

Variable	Questionnaire	Time of administration
March Capacity	RNFC scale	Entry, at 6 weeks, 4 months and 1 year.
	The walking capacity assessment scale (mFAC).	Entry, at 6 weeks, 4 months and 1 year.
Physical capacity	Barthel Index	At 6 weeks, 4 months and 1 year.
	Oxford Hip Score Scale	At the 1st, 3rd, 6th and 12th month.
Sarcopenia	SARC-F Scale	At 6 weeks, 4 months and 1 year.
Adverse Events	STRATIFY scale	At 6 weeks, 4 months and 1 year.
	Medical complications (ad hoc questionnaires)	At 6 weeks, 4 months and 1 year.
Quality of life	Questionnaire EQ-5D-5L	At the 1st, 3rd, 6th and 12th month.

- The functional recovery programme designed and implemented as standard practice from 1 January 2021. This programme consists of a series of presentations and videos, in simple language with information and recommendations. It will provide answers to patients' most frequently asked questions and will also allow patients to receive reminders regarding their care (recommended exercises, precautions to take in certain circumstances, alerts, etc.).

It is the clinician and the patient, or family member if applicable, who enters the data directly into the application, prior to accepting the legal clauses to that effect.

The study variables collected in the project are included among the clinical variables included in the orthogeriatric protocol for the care of hip fracture patients at the HSJD. In order to analyse those established for this study, the variables will be extracted from the data collection platform, the PI being responsible for the storage and processing of the data in accordance with current legislation.

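### Followed as written, the 2021 recovery rate describes surviving, compliant attenders, because death, withdrawal and missed visits have no rule in the mobility outcome

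*Combined protocol and SAP*

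**What the plan says.** The overall objective is return to the functional state before the fracture. Among the listed function measures, only RNFC and mFAC are taken both on entry and later; the Barthel Index starts at 6 weeks (Table III). For RNFC the text below Table I says "This scale is administered at admission, 6 weeks, 4 months and 1 year", mFAC has the same schedule, and Table III repeats "Entry, at 6 weeks, 4 months and 1 year".

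Under Variables, the new model has two follow-up tracks. In the clinic, "patients will be followed up in person at one and a half months, four months and one year". Through the app, contacts come at discharge and at 1, 3, 6 and 12 months; Table III places only the Oxford Hip Score and EQ-5D-5L on the 1, 3, 6 and 12 month dates. The Data collection procedure says the 2021 data "will be collected by the trauma team during scheduled patient follow-up visits"; the same sentence adds entry by the patient or caregiver through the app, without assigning scales to either route.

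RNFC ends at level 10 (which includes no mobility) and level 11 (unknown). mFAC runs from 0 to 6. Death appears as an adverse-event code, and mortality is a separate specific objective.

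The withdrawal criteria for the 2021 cohort are in-hospital death, complications, and non-compliance with the plan or the assessments. None are listed for 2020. The Sampling section nevertheless promises an analysis of the entire 2021 cohort.

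For earlier practice, the Variables section says "Until now, data collection and patient follow-up was completed after one month". For the 2020 mobility scales, "data will be retrieved from the Exceldata collection system that the medical management of the HSJD manages".

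The paragraph on analysis of results (Work plan) gives summary statistics and tests for baseline characteristics. It states no outcome analysis set, and no rule for missing visits, for RNFC level 11 or for death.

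**The concern.** Whether a patient has a recovery result can depend on how well that patient recovered. The Justification describes a rural population, far from people who could help, with "difficulties in accessing the different resources to achieve an optimal recovery". That sentence is about recovery resources rather than clinic attendance, but it makes it reasonable to expect the poorest walkers to attend least. If so, the 2021 recovery rate is likely too high.

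Two further mechanisms affect any comparison with 2020, and they pull in opposite directions. Withdrawal for complications or non-compliance removes patients who probably recover less often, and from one cohort only, so it favours the programme. Survival can work against it. The Introduction reports that "multidisciplinary rehabilitation was associated with a modest but significant reduction in adverse outcomes such as death", so a survival difference is an effect the plan has in view. If frail patients are kept alive and only survivors are scored, the programme cohort gains people with poor mobility and its rate falls although nobody was harmed.

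At stake are the 2021 recovery rate and the size, possibly the sign, of the contrast that answers the overall objective.

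**Working it through.** The plan states no attendance, mortality or recovery rate by cohort, so there is no figure of its own to reproduce. The one anchor is the Introduction's 50% recovery, whose denominator (survivors or all patients) is not given. Every other input below is assumed.

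**1. Attendance, 2021 cohort alone.** True recovery 50%; attendance 90% if recovered and a if not. Observed recovery = 0.50 × 0.90 / (0.50 × 0.90 + 0.50 × a).

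| a | Calculation | Observed recovery |
|---|---|---|
| 80% | 0.45 / 0.85 | 52.9% |
| 70% | 0.45 / 0.80 | 56.3% |
| 60% | 0.45 / 0.75 | 60.0% |

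**2. One-sided withdrawal, no true effect.** Both cohorts truly recover at 50%. A share c of the 2021 cohort, recovering at rate q, is removed. Remaining rate = (0.50 − c × q) / (1 − c).

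- c = 10%, q = 40%: 0.46 / 0.90 = 51.1% (+1.1 points)
- c = 20%, q = 25%: 0.45 / 0.80 = 56.25% (+6.25 points)
- c = 30%, q = 10%: 0.47 / 0.70 = 67.1% (+17.1 points)

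**3. Survivors only, where the programme does nothing except save lives.** Let m be 2020 mortality, s the extra share kept alive and r their recovery rate, with 50% recovery among 2020 survivors. Programme rate among survivors = (0.50 × (1 − m) + s × r) / (1 − m + s), against 50%. With death counted as not recovered, the comparison is 0.50 × (1 − m) + s × r against 0.50 × (1 − m).

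- m = 20%, s = 10%, r = 10%. Survivors only: 0.41 / 0.90 = 45.6% against 50.0% (−4.4 points). Death as not recovered: 41.0% against 40.0% (+1.0 point).
- Over m 10–30%, s 5–10%, r 0–25%, the survivors-only difference runs from −1.3 points (0.4625 / 0.95 = 48.7%) to −6.25 points (0.35 / 0.80 = 43.75%). With death as not recovered it equals s × r, which is 0 to +2.5 points.

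**4. Both together.** Take m = 20%, s = 5%, r = 10%, and withdraw a share c of the operated 2021 cohort from among its survivors. Rate = (0.405 − c × q) / (0.85 − c), against 50%.

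- c = 5%, q = 25%: 0.3925 / 0.80 = 49.1% (−0.9 points)
- c = 5%, q = 10%: 0.400 / 0.80 = 50.0% (no difference)
- c = 20%, q = 10%: 0.385 / 0.65 = 59.2% (+9.2 points)

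Steps 2 to 4 need mobility data from both cohorts at the same time point. The documents place the end of 2020 follow-up at one month, so they do not show such data at 6 weeks, 4 months or 1 year.

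**The case against.** The strongest reply is that much of this comes from silence. The documents nowhere say that the mobility scales can be scored only face to face. The app has a patient or carer profile as well as a doctor profile, its questionnaires are described by reference to Table III, and Table III includes RNFC and mFAC. RNFC is also reduced to simple questions that a carer could answer, and at 12 months the clinic and app contacts coincide. This stands: in-person scoring is an inference from matching dates and from the description of face-to-face entry. What remains is that no remote route is stated for a missed visit, and that no app questionnaire is scheduled at 6 weeks or 4 months.

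A second reply is that no survivors-only analysis is written down, deaths are recorded separately, and the plan promises the whole cohort. That is true, but the withdrawal criteria contradict that promise, and nothing says how a recorded death enters the recovery outcome.

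Third, a reader might infer that the plan will make a life-saving programme look worse at one year. The documents do not support that. The section introducing the second group of variables says they can be measured only in the 2021 cohort, and Table II puts follow-up RNFC and mFAC there. The one-sided withdrawals also push the other way and may be larger. Finally, lower attendance among poor walkers and all the mortality inputs are assumptions, and the cited reduction in adverse outcomes is described as modest.

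**Conclusion.** The point holds in a limited form. The mobility follow-up dates are the clinic dates, no fallback for a missed visit is stated, neither scale can record death, and the withdrawal rules remove patients from one cohort only. Followed as written, this gives a 2021 recovery rate among surviving, compliant attenders and conflicts with the promised whole-cohort analysis. With 50% true recovery and the assumed attendance pattern, the overstatement is about 3 to 10 points.

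For a comparison with 2020 the direction is not fixed. Under the stated assumptions, withdrawal alone gives +1.1 to +17.1 points, survivors-only scoring alone −1.3 to −6.25, and the combined examples −0.9 to +9.2. Reversal of a survival benefit is therefore possible, but it is not the predicted result, and the contrast applies only at time points for which both cohorts have data. Either direction calls for the same remedy, which should be settled before analysis.

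**What to change.** 1. Keep all eligible operated patients in the analysis of both cohorts. Treat the listed withdrawal events as outcomes or as stopping the programme, not as removal from the analysis, and reconcile the withdrawal criteria with the Sampling section.
2. Define recovery at each time point as alive and at or better than the pre-fracture RNFC level. Count death as not recovered, under the same rule in both cohorts wherever data exist. Show survivors only as a secondary result, and report deaths and missing visits by cohort and time point. Treat RNFC level 11 as missing, not as a mobility level.
3. When a visit is missed, obtain RNFC from the patient or carer by app or telephone at the same date. Add it to the 12-month app contact, and flag the mode of collection.

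The cost is a few sentences of analysis wording, one app item and some calls. The downside is a mixed collection mode, which the flag makes visible and lets the analysis examine. None of this creates 2020 data beyond what the hospital file holds; the plan should state which time points that file supports.
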